16.1 Adverse events

The crude incidence of treatment emergent adverse events on secukinumab (i.e. events started after the first dose of secukinumab in core study or events present prior to the first dose of secukinumab but increased in severity based on preferred term and within 84 days after last dose of secukinumab) will be summarized by primary system organ class and preferred term for the entire treatment period. CIs for the crude rate will be derived as described in [Section 19.3.3](#).

In addition, exposure time-adjusted rates (incidence rate) including 95% CIs will be provided for selected terms for the entire treatment period (see [Section 19.3.5](#)) to adjust for differences in exposure.

Adverse events reported will be presented in descending frequency according to the incidence in total secukinumab group (combining all secukinumab treatment groups) starting from the most common event.

Summary statistics will be provided by primary system organ class and preferred term for the entire treatment period for all TEAEs, for serious TEAEs, for deaths, for TEAEs causing treatment discontinuation, for TEAEs possible related to study treatment, for TEAEs leading to temporary dose interruptions, for other serious or clinically significant treatment emergent adverse events or related discontinuations, for SPP risks and for adjudicated major adverse cardiovascular events (MACE). Additionally, summary statistics by 26 and 52 weeks intervals will be displayed reflecting the long term safety. For these tables the AEs will be counted only at the interval they were initially observed. If another AE with the same PT is starting again in a following time interval then it will be counted again at this interval.

Summaries (crude incidence only) will be presented for TEAEs by maximum severity as well. If a particular AE 'severity' is missing, this variable will be listed as missing and treated as missing in summaries.

If a subject reported more than one adverse event with the same preferred term, the adverse event with the greatest severity will be presented. If a subject reported more than one adverse event within the same primary system organ class, the subject will be counted only once with the greatest severity at the system organ class level, where applicable.

Adverse events separately by SMQ according to MedDRA using a narrow search will also be reported..

Exposure adjusted incidence rates for TEAEs by SMQ and preferred term, for selected lower lever risk terms based on TEAEs, serious adverse events, SPP risks and MACE, common and/or very common AE will be summarized by primary system organ class for the entire period.

The following AE terms are defined as lower lever risk terms:

- Dyspnea (PT)
- Seasonal allergy (PT)
- Colitis ulcerative (PT)
- Crohn's disease (PT)
- Inflammatory bowel disease (PT)
- Upper respiratory tract infections (HLT)
- Candida infections (HLT)
- B-cell lymphoma (PT)
- Bladder transitional cell carcinoma (PT)
- Breast cancer (PT)
- Lymphoma (PT)
- Malignant melanoma (PT)
- Dermatitis (PT)
- Eczema (PT)
- Rash(PT)
- Leukopenia (PT)
- Neutropenia (PT)
- White blood cell count decreased (PT)
- Dyspnea (PT)
- Seasonal allergy (PT)
- Diarrhea Hemorrhagic (PT)
- Squamous cell carcinoma (PT)
- Urticarial (PT)
- Uveitis (PT)
- Drug related hepatic disorders – severe events only (SMQ)(broad)
- Liver related investigations, signs and symptoms (SMQ) (broad)

The above list maybe modified based on the clinical team's advice.

As selection criterion for the common AE is the frequency of them of at least 2% in the initial treatment period (up to week 16) or IR of at least 5 during the entire treatment period as observed in the Any AIN457 group. The very common AE are defined in Core Data Sheet V2.1 (17-Mar-2017), Table 7.1. These include the following PTs: Nasopharyngitis, Upper respiratory tract infection, Rhinitis, Pharyngitis, Oral herpes, Rhinorrhoea, Diarrhea, Urticaria.

The incidence of AEs will be presented per 100 subject years of exposure.

The MedDRA version used for reporting the study will be described in a footnote.

If needed, follow-up period summaries will be done for all subjects in follow-up in this extension study (completers and early discontinuations).

AE listings will be limited to deaths, non-fatal SAEs, AE requiring treatment discontinuations and adjudicated MACE events.

Algorithms for date imputations in the AE listings are provided in PDS.

When adjudication is required of major cardiovascular events, a summary of those types of events as reported by the investigator and confirmed by adjudication will be provided.

Listings will be provided for all adverse events, all non-fatal serious adverse events, deaths, adverse events leading to discontinuation from study treatment or temporary dose interruption, adverse events by SPP risks and adjudicated MACE events (myocardial infarctions, strokes, and cardiovascular deaths).

The safety analyses and which will be performed for treatment emergent AEs, labs, ECG and vital signs are described in [Table 16-1](#) below.

Table 16-1 Overview of analyses on major safety endpoints

Analysis period	AEs & SAEs	AEs severity	by	Study drug related AEs	AEs-SMQ	SPP Risk	Notables for (vitals/ ECG), lab criteria
Entire treatment period	
• crude incidence• exposure time adjusted incidence*	
• crude incidence		
• crude incidence	
• exposure time adjusted incidence*	
• crude incidence• exposure time adjusted incidence*	
• crude incidence

*Exposure-adjusted incidence rates will be done for the following:

- at the PSOC for AE and SAE
- at the PT level for common AEs, which is defined as at least 2% of the patients in the combined AIN457 groups during the initial treatment period or events that had an incidence rate of at least 5.0 cases per 100 subject-years in the combined AIN457 groups during the entire treatment period
- at Level 1 for Risks and SMQ analyses

For the legal requirements of ClinicalTrials.gov and EudraCT, two required tables on <treatment emergent> adverse events which are not serious adverse events with an frequency greater than 5% and on <treatment emergent> serious adverse events and SAE suspected to be related to study treatment will be provided by system organ class and preferred term on the safety set population.

The tables will include data based on the safety population.

If for a same patient, several consecutive AEs (irrespective of study treatment causality, seriousness and severity) occurred with the same SOC and PT:

- a single occurrence will be counted if there is ≤ 1 day gap between the end date of the preceding AE and the start date of the consecutive AE
- more than one occurrence will be counted if there is > 1 day gap between the end date of the preceding AE and the start date of the consecutive AE

For occurrence, the presence of at least one SAE / SAE suspected to be related to study treatment / non SAE has to be checked in a block e.g., among AE's in a ≤ 1 day gap block, if at least one SAE is occurring, then one occurrence is calculated for that SAE.

The number of deaths resulting from SAEs suspected to be related to study treatment and SAEs irrespective will be included.

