3.4 Rationale for choice of comparator

There is no placebo or active control group in this study given the purpose and main objectives are to extend treatment of subjects who completed the core study. The use of two different doses of secukinumab (i.e. 75 and 150 mg) will allow comparison between the doses in terms of sustainability of clinical benefits, safety and tolerability.

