Additional analysis will be based on the imputed responses only for the AIN457 150 mg group.

[figure not shown]
The percentage of subjects (and the 95% CI) experiencing ASAS40 response after up-titration will be presented in separate tables (observed data). Patients who had at least 1 dose of the up-titrated dose will be included.

16 Safety evaluation

Safety analyses will be done on the safety set.

Analysis of adverse events will be based on treatment emergent events, which are defined as events started after the first dose of study treatment in core study or events present prior to the first dose of study treatment in core study but increased in severity based on preferred term and within last dose + 84 days.

Other safety variables will be based on on-treatment events, which are defined as any events that happened after first dose of study treatment and within last dose + 84 days.

Summaries (other than by visit analysis) will be presented cumulatively from core and extension. For subjects who switched from placebo to secukinumab in the core study, their data prior to switch will not be reported. Safety on placebo will be based on the core study and will be reported in the in-text outputs and study listings.

Unless otherwise mentioned, by visit analysis will include the following visits: Baseline visit from core, Week 104E1 visit and all visits in extension. Summaries will be performed for all the events that happened within the last dose + 84 days.

Safety analyses will be performed on treatment received or actual treatment as described below:

The actual treatment or treatment received for summaries of safety data will differ to the treatment assigned at randomization if a subject received the wrong treatment during the entire study or if the subject up-titrated to a higher dose..

Subjects who switch treatment during the study (e.g. from placebo to active treatment, or escalated the dose) will be counted to both groups using the corresponding start and stop exposure date.

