16.3 Vital signs

The summary of vital signs will only include on treatment data, which are defined as those vital sign measurements after the first dose of study treatment and on or before last dose + 84 days.

Analysis in vital sign measurement using descriptive summary statistics for the change from baseline for each post-baseline visit in extension will be performed. These descriptive summaries will be presented by vital sign and treatment dose. Change from baseline will only be summarized for subjects with both baseline and post-baseline values and will be calculated as: change from baseline = post-baseline value – baseline value

The number and percentage of subjects with newly occurring notable vital signs will be presented. Criteria for notable vital sign abnormalities are provided in [Table 16-4](#) below.

Table 16-3 Criteria for notable vital sign abnormalities

Vital sign (unit)	Notable abnormalities
Systolic blood pressure (mmHg)	≥ 140 mmHg or < 90 mmHg
Diastolic blood pressure (mmHg)	≥ 90 mmHg or < 60 mmHg
Pulse (bpm)	> 100 bpm or < 60 bpm

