16.4 Electrocardiogram (ECG)

The summary of ECG will only include on treatment data, which are defined as those ECG measurements after the first dose of study treatment and on or before last dose + 84 days.

The following quantitative variables will be summarized: ventricular rate, RR interval, PR interval, QRS duration, QT interval, and corrected QT interval (QTc). Both Bazett (QTcB) and Fridericia (QTcF) corrections will be presented for QTc.

QTc will generally be summarized by computing the number and percentage of subjects (including 95% CIs for pooled analyses, e.g. DMC or SCS) with:

- QTc > 500 msec
- QTc > 480 msec
- QTc > 450 msec
- QTc changes from baseline > 30 msec
- QTc changes from baseline > 60 msec
- PR > 250 msec

Summary statistics will be presented by visit and treatment dose in safety population.

Subjects with notable abnormal ECG parameters as described above, after baseline will be summarized.

Shift tables comparing baseline ECG interpretation (normal, abnormal, not available, total) with the worst on-study interpretation (normal, abnormal, not available, total), listing of all newly

occurring or worsening abnormalities, as well as a by-subject listing of all quantitative ECG parameters.

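### Severity tables and notable lab, vital-sign and ECG values are planned as crude percentages only, and the rate for drug-related and discontinuation AEs is unclear, although escalation gives the 75 mg and 150 mg columns unequal observation windows

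*SAP*

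**What the plan says.** SAP 5.2 sets the safety columns by dose: Any AIN457 75 mg, Any AIN457 150 mg and Any AIN457. SAP Section 16 makes the summaries (other than by-visit ones) cumulative over core and extension and adds: "Subjects who switch treatment during the study (e.g. from placebo to active treatment, or escalated the dose) will be counted to both groups", with exposure dates applied separately for each treatment. Protocol 5.5.5 allows escalation at any site visit after Amendment 1 and rules out a later reduction.

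SAP 16.1 adds exposure-adjusted rates for selected terms "to adjust for differences in exposure". The footnote to Table 16-1 in that section (the overview of safety endpoints, not the CTCAE table that carries the same number) limits them to "at the PSOC for AE and SAE", common preferred terms, and level 1 of the risk and SMQ analyses. By output:

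- **AEs by maximum severity.** Crude in the table and in the text: "Summaries (crude incidence only) will be presented for TEAEs by maximum severity as well".
- **Study-drug-related AEs.** The table lists crude incidence as the only measure.
- **Notable values.** The column "Notables for (vitals/ ECG), lab criteria" lists crude incidence alone. The text agrees: "The number and percentage of subjects with newly occurring notable vital signs will be presented" (16.3) and "QTc will generally be summarized by computing the number and percentage of subjects" (16.4).
- **AEs leading to discontinuation or interruption.** Summaries are planned, but no exposure-adjusted rate is named for them.

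Against this, SAP 16.1 and Protocol 9.5.2 both contain an unrestricted sentence giving AE incidence per 100 subject-years.

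**The concern.** Escalation closes a subject's 75 mg window early and adds the same subject to the 150 mg denominator with a late, short window. A crude percentage ignores window length. Early escalation mainly shortens 75 mg follow-up, so 150 mg looks worse. Late escalation mainly fills the 150 mg denominator with short windows, so 75 mg looks worse.

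Protocol 3.4 says that having two doses "will allow comparison between the doses in terms of sustainability of clinical benefits, safety and tolerability". The affected tables are ones a reader would consult for tolerability. Part of any difference in them, or of its absence, may reflect only who escalated and when, and a crude percentage does not show how much.

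**Working it through.** **The plan's own figures.** Core size is not stated. Back-solving the expected extension entry (SAP Section 18: 75% to 85%, about 279 to 316) gives 279/0.75 = 372.0 and 316/0.85 = 371.8, so 372 is consistent with both ends. The exposure example in SAP Table 19-3 also reproduces: an event on day 110 after 100 days of placebo gives 110 − 100 = 10 days on 150 mg.

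**Inputs.** From the documents: last dose at Week 256 and follow-up at Week 268 (Protocol 5.5.11, 3.1), and one-way escalation. Assumed: equal numbers initially on each dose; 80% entering the extension; non-entrants observed for 60 weeks; no further dropout; no allowance for the core placebo period; a constant event rate r, the same on both doses; share f of extension subjects on 75 mg escalating at week e.

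**Formulas.** With P(w) = 1 − exp(−r·w/52.18), w in weeks and r per subject-year:

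- Crude 75 mg = 0.2·P(60) + 0.8(1−f)·P(268) + 0.8f·P(e)
- Crude 150 mg = [0.2·P(60) + 0.8·P(268) + 0.8f·P(268−e)] / (1 + 0.8f)

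**Example: r = 0.10, f = 0.4, e = 116.** P(60) = 0.1086, P(116) = 0.1993, P(152) = 0.2527, P(268) = 0.4017.

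- 75 mg: 0.0217 + 0.48 × 0.4017 + 0.32 × 0.1993 = 0.278
- 150 mg: (0.0217 + 0.8 × 0.4017 + 0.32 × 0.2527) / 1.32 = 0.321

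**Crude % (75 mg vs 150 mg) at a true 10 per 100 subject-years on both doses**

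| Share escalating | Week 116 | Week 156 | Week 208 |
|---|---|---|---|
| 20% | 31.1 vs 33.1 | 32.0 vs 32.2 | 33.1 vs 31.1 |
| 40% | 27.8 vs 32.1 | 29.7 vs 30.7 | 32.0 vs 28.6 |
| 80% | 21.4 vs 30.8 | 25.1 vs 28.5 | 29.6 vs 25.2 |

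Over 20-40% escalating at these weeks, the absolute gap runs from 0.1 to 1.1 points at 2 per 100 subject-years, 0.2 to 2.5 at 5, and 0.2 to 4.3 at 10. The ratio of mean subject-years per subject (75 mg over 150 mg) spans 0.65 to 1.16 over 20-80% escalating.

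**Second model, with and without dropout.** Take a 260-week horizon, equal columns and no dropout. The mean windows are then T − f(T−t) for 75 mg and [T + f(T−t)]/(1+f) for 150 mg. They are equal at t = T − T/(2+f), which is Week 136, 147 or 156 for f = 10%, 30% or 50%. At rate 10 and f = 50%, the gap (150 minus 75 mg) is +6.1, −0.4 and −6.7 points for escalation at Weeks 104, 156 and 208. With dropout calibrated to 80% retention at Week 104 it becomes +4.8, +0.5 and −3.3. Dropout shrinks the larger gaps, but the sign still changes with escalation time.

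**Effect of the SAP's own rate.** Applying D/T from SAP 19.2.5, with time to first event inside each column's own window, to the same no-dropout scenarios returns 10.00 vs 10.00 per 100 subject-years. Under a constant rate the artefact disappears.

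**The case against.** The strongest reply is that much of this is covered elsewhere and the rest is small.

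- **Interval summaries.** SAP 16.1 plans 26- and 52-week interval tables directly after a list that includes related, discontinuation and interruption AEs. This helps in part, but they name neither severity nor notable values and have no denominator rule.
- **The per-100-subject-year sentence.** A reader might infer that all these outputs are plainly crude-only. For related and discontinuation AEs the documents do not support that: they contain a conflict to be reconciled. The general sentence does not override the explicit severity restriction, and notable values are not as such AEs.
- **Other safety outputs.** SAEs, MACE, SPP risks and selected blood-count and liver terms already get exposure-adjusted rates. Clinically significant laboratory values and clinically relevant ECG changes are reported as AEs (Protocol 7.1, 6.5.5) and so reach the SOC-level rates. By-visit summaries do not accumulate risk. Exposure duration by group is also planned (SAP Section 10). All this stands and limits the damage, but it does not supply the missing rates.
- **Size.** A reader might infer that equal risks will show as a dose difference, or that escalation alone sets its size. Neither follows. Several scenarios give almost no gap, and event rate and dropout matter too. With an assumed 186 subjects per column (372/2), the SAP 19.2.3 score interval around 20% is about 14.6% to 26.6%, wider than many of these gaps.
- **Descriptive purpose.** No hypothesis is tested and the safety objective is overall safety. The risk is therefore misreading, not type I error.

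**Conclusion.** The point holds as a reporting defect of moderate weight. The SAP recognises unequal exposure and has a method for it, but withholds that method from severity and notable values and leaves related, discontinuation and interruption AEs unclear. At equal risk the crude dose columns can differ in either direction.

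For events at 2 to 5 per 100 subject-years with 20-40% escalating, the model gives gaps of about 0.1 to 2.5 points. At 10 per 100 subject-years it gives up to 4.3. With 80% escalating, gaps at that rate reach 9.4 points one way (Week 116) and about 4.5 the other (Week 208). These figures rest on assumed escalation, a constant common rate and no dropout after extension entry.

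It would also be tempting to conclude that exposure-adjusted rates make the doses comparable. They do not. Escalated person-time comes late and is selected by the investigator for incomplete response, and the adjustment is exact only under a constant rate.

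**What to change.** In SAP 16.1 and its Table 16-1:

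1. Replace the restriction to crude incidence for severity. Add the SAP 19.2.5 rate with 95% CI (16.1 cites it as 19.3.5), using each dose's own exposure window as in Table 19-3, for severe TEAEs, study-drug-related TEAEs, and TEAEs leading to discontinuation or to interruption. Overall and SOC level are enough.
2. Reconcile Table 16-1 with the per-100-subject-year sentence in SAP 16.1 and Protocol 9.5.2, so that each AE output has one stated measure.
3. For newly occurring notable laboratory, vital-sign and ECG values, print subject-years beside the crude percentage and give the same rate per criterion. Note that onset is known only to the scheduled visit; in the extension these visits are roughly 12 to 28 weeks apart.
4. Footnote these tables: the rates adjust for window length under a constant-rate assumption and do not remove selection or calendar-time differences in escalated person-time.

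The cost is SAP wording and more output. No new data are needed, the method is already specified, and no treatment rule changes.

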9.5.2 Safety variables

Adverse events

Treatment emergent adverse events (events started after the first dose of study treatment in the extension or events present prior to the first dose of study treatment in core study but increased in severity based on preferred term and within 84 days after last dose of secukinumab) will be summarized.

AEs will be summarized by presenting, for each treatment group, the number and percentage of subjects having any AE, having an AE in each primary system organ class and having each individual AE (preferred term). Summaries will also be presented for AEs by severity and for study treatment related AEs. If a subject reported more than one adverse event with the same preferred term, the adverse event with the greatest severity will be presented. If a subject reported more than one adverse event within the same primary system organ class, the subject will be counted only once with the greatest severity at the system organ class level, where applicable. Serious adverse events will also be summarized.

The incidence of AEs will be presented per 100 subject years of exposure.

Separate summaries will be provided for death, serious adverse event, other significant adverse events leading to discontinuation and adverse events leading to dose adjustment (including study treatment discontinuation).

A graphical display of relative frequencies within system organ classes and relative risks, as appropriate, will be presented.

When adjudication is required of major cardiovascular adverse events, a summary of those types of events as reported by the investigator and confirmed by adjudication will be provided.

Laboratory data

The summary of laboratory evaluations will be presented for three groups of laboratory tests (hematology, serum chemistry and urinalysis). Descriptive summary statistics for the change from baseline to each study visit will be presented. These descriptive summaries will be presented by test group, laboratory test and treatment group. Change from baseline will only be summarized for subjects with both baseline of core study and post baseline values.

For each parameter, the maximum change from baseline within each study period will be evaluated analogously.

[figure not shown]

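### SAP 16.1 gives preferred terms outside fixed lists an exposure-adjusted rate only above a frequency cut-off, leaving some fairly frequent terms with crude percentages that do not compare fairly between doses

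*SAP*

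**What the plan says.** Protocol 9.5.2 makes an unqualified statement: "The incidence of AEs will be presented per 100 subject years of exposure". SAP 16.1 repeats it, but also says that exposure-adjusted rates with 95% CIs "will be provided for selected terms for the entire treatment period", the stated purpose being to adjust for differences in exposure.

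SAP 16.1 selects the terms in two places.

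- **Main text.** Common AEs qualify at "at least 2% in the initial treatment period (up to week 16) or IR of at least 5 during the entire treatment period", judged in the Any AIN457 group. Rates are also planned, whatever the frequency, for a named list of risk terms, SPP risks, MACE and eight very common preferred terms ("The very common AE are defined in Core Data Sheet V2.1 (17-Mar-2017), Table 7.1"). The governing sentence opens "Exposure adjusted incidence rates for TEAEs by SMQ and preferred term, for selected lower lever risk terms based on TEAEs, serious adverse events" and ends by saying that the summaries are by primary system organ class.
- **Footnote to the overview table of safety analyses (Table 16-1).** Rates are given at primary system organ class for AEs and SAEs, at Level 1 for risks and SMQs, and "at the PT level for common AEs, which is defined as at least 2% of the patients in the combined AIN457 groups" in the initial treatment period. The second limb for common AEs is an "incidence rate of at least 5.0 cases per 100 subject-years in the combined AIN457 groups during the entire treatment period".

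All TEAEs get crude incidence by preferred term with CIs over the entire treatment period. Summaries by 26- and 52-week interval are added to show long-term safety.

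SAP 5.2 presents safety as Any AIN457 75 mg, Any AIN457 150 mg and Any AIN457. SAP 16 counts subjects who escalate in both dose groups, split at the exposure dates. SAP 1 says that deviations from the protocol are documented. SAP 2 does not mention this restriction.

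**The concern.** Long-term safety is a secondary objective, and safety is displayed by dose. Exposure to the two doses is unequal by design: escalation goes only from 75 mg to 150 mg, so a subject's 75 mg time stops there and 150 mg time begins. Subjects also leave at different times. A crude percentage takes no account of time at risk, so two dose groups with the same hazard can show different percentages. SAP 16.1 recognises this as the reason for exposure adjustment, then withholds the adjustment from terms that are neither listed in advance nor above the cut-off.

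The fixed lists reflect risks already known. A new term can join the risk list only at the clinical team's discretion. For SAEs, the footnote gives rates only by system organ class, where one preferred term can be diluted by others, and the main text is unclear.

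**Working it through.** **1. Core sample size.** Protocol 9.7 and SAP 18 give 279 to 316 subjects as 75% to 85% of the core study. 279/0.75 = 372.0 and 316/0.85 = 371.8, so both figures fit a core N of about 372.

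**2. Which limb is easier to meet.** At a constant hazard, 2% by Week 16 (112/365.25 = 0.3066 years) is -ln(0.98)/0.3066 = 6.6 per 100 subject-years (6.5 by simple division). The limb of 5 per 100 is therefore the working threshold. A term at 4.9 per 100 reaches 1 - exp(-0.049 × 0.3066) = 1.5% by Week 16 and fails both.

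**3. Subject-years on secukinumab.** The documents give no retention figures. Assumptions: 75-85% enter the extension, 80-90% of those are retained to its end, losses are linear, and one third of core subjects spend 20 weeks on placebo (124 × 140/365.25 = 48 years).

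| | Low | High |
|---|---|---|
| Core: 372 × 2 × (1 + entry)/2 | 651 | 688 |
| Extension: 372 × entry × 3 × (1 + retention)/2 | 753 | 901 |
| Less placebo | 48 | 48 |
| Total | about 1,357 | about 1,542 |
| Mean per subject (total/372) | 3.65 years | 4.14 years |

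**4. Subjects affected just below the cut-off.** SAP 19.2.5 stops time at the first event, so the expected count is 372 × [1 - exp(-0.049 × mean years)].

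- Low: 372 × [1 - exp(-0.179)] = 61 (16%).
- High: 372 × [1 - exp(-0.203)] = 68 (18%).

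With complete five-year follow-up, a hazard of 5 per 100 gives 1 - exp(-0.25) = 22%. That is an upper bound.

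**5. What the omitted rate would look like.** Exposure to first event is 61/0.049 ≈ 1,242 and 68/0.049 ≈ 1,395 subject-years (using unrounded counts). The exact Poisson interval in SAP 19.2.5 gives 4.9 per 100 (95% CI 3.8 to 6.3) and 4.9 (3.8 to 6.2). The plan as written gives crude 61/372 = 16.4% (12.9 to 20.6) and 68/372 = 18.3% (14.6 to 22.7), by the score method in SAP 19.2.3. Precision is not a reason to leave the rate out.

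**6. Why the crude figure misleads between doses.** Illustration with an identical hazard of 3 per 100 and assumed mean exposures of 3 and 4.5 years: 1 - exp(-0.09) = 8.6% against 1 - exp(-0.135) = 12.6%. The difference comes from follow-up alone.

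**7. Events that occur only in the extension.** Ignoring first-event censoring, the extension rate needed to reach 5 per 100 overall is 5 × 1,357/753 = 9.0 or 5 × 1,542/901 = 8.6 per 100. Such events can qualify, but the bar is higher.

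**The case against.** The strongest reply is that little is really missing, and much of it stands.

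- A reader might infer that a filtered term gets no rate or CI at all. It does not follow: crude incidence with a CI is planned for every preferred term.
- A reader might infer that the filter removes late-emerging events in particular. The documents do not support that. The two limbs are joined by "or", so the Week 16 limb can only add terms. The other limb covers the entire period. The interval summaries show late onset directly.
- Many terms get rates whatever their frequency, and so does every system organ class. The risk list may also be modified. What remains is narrow: terms outside every list and below both limits.
- Removing the filter would not cure the averaging of late events over earlier years. SAP 19.2.5 assumes a constant intensity, so a whole-period rate stays diluted.
- Protocol 9.5.2 names no MedDRA level, so rates by system organ class could be said to satisfy it.
- Exposure by group is reported, so a reader could divide counts by subject-years. In the example this gives 61/1,357 = 4.5 per 100 instead of 4.9, with no interval.

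One point remains unanswered. Neither a CI around a crude percentage nor the interval summaries, for which no exposure adjustment is specified, correct for unequal exposure between the dose groups.

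**Conclusion.** The concern holds in a limited form. Preferred terms outside the fixed lists and below both limits get no exposure-adjusted rate, even at about 16-18% of subjects. Their crude percentages cannot fairly be compared between Any 75 mg and Any 150 mg. The two parts of SAP 16.1 also need reconciling for SAEs, and the filter sits beside an unqualified statement of incidence per 100 subject-years that appears in both documents.

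The 16-18% rests on an inferred core N of 372, a constant hazard, the assumed entry, retention and placebo time, and mean follow-up applied to everyone. The 3-year and 4.5-year exposures are illustrative only, since the documents do not say how many subjects escalate or when. No hypothesis test is affected. This is an inexpensive improvement to the main long-term safety display and does not invalidate the plan.

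**What to change.** - Remove the common-AE condition from the exposure-adjusted tables. Produce the rate with its exact 95% CI by SAP 19.2.5 for every preferred term, for TEAEs and for SAEs, in each dose group and in Any AIN457.
- If length matters, restrict only the in-text display, for example to terms in at least 1% of Any AIN457 subjects at any time, and keep the full table in the appendix.
- Make the main text of SAP 16.1 and the table footnote agree on the level at which SAE, risk and SMQ rates are given. If any filter is kept, record it in SAP 2 as a change from Protocol 9.5.2.
- Correct the cross-references in SAP 16.1 to Sections 19.3.3 and 19.3.5. The methods are in 19.2.3 and 19.2.5.
- Keep the 26- and 52-week summaries as the display of timing.

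The cost is one condition removed from a program that is already planned, and a longer table with wide CIs for rare terms.
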